### 2.3.2 KNOWN POTENTIAL BENEFITS

There is no expected clinical benefit for the healthy subjects that will participate in this study. Overall, on the basis of the available non-clinical and clinical data, and prior knowledge, the risk-benefit profile of OZ439 and PQP are judged acceptable for the proposed clinical study.

### 3 OBJECTIVES AND PURPOSE

#### Primary:

- a) To characterize the PK/PD relationships between OZ439 and PQP plasma concentrations and blood stage asexual parasitaemia in healthy subjects following *P. falciparum* IBSM infection.
- b) To evaluate the safety and tolerability of OZ439 and PQP when administered as single doses in healthy subjects following *P. falciparum* IBSM infection

#### Secondary:

- a) To describe the PK of OZ439 and PQP when administered as single doses in healthy subjects under fasted conditions.
- b) To characterize the PD effect of administered single doses of OZ439 and PQP on clearance of *P. falciparum* asexual blood stage parasites from the blood of healthy subjects in the IBSM model.

#### Exploratory:

The exploratory study objectives are:

- a. To characterise specific cell subsets and immune signatures associated with control of parasite burden and pathogenicity following first exposure to *P. falciparum*, to identify specific cells, immunomodulatory molecules and immune pathways to target for therapeutic intervention.
- b. To investigate the role of RBC complement regulatory proteins and anti phosphatidylserine antibodies in malarial anaemia.
- c. To investigate the association between serum complement activation, complement activating antibodies, and RBC complement regulatory protein expression.

## 4 STUDY DESIGN AND ENDPOINTS

### 4.1 DESCRIPTION OF THE STUDY DESIGN

This is a single centre, open label, adaptive study using the *P. falciparum* IBSM inoculum as a model to characterise the PD activity of combined administration of OZ439 and PQP.

The study will be conducted in a maximum of three cohorts (up to 8 subjects per cohort) using up to 4 different doses of OZ439 and PQP in each cohort. Subjects will be malaria naïve healthy males or females, aged between 18-55 years old, who meet all of the inclusion criteria and none of the exclusion criteria. Additionally, the study includes optional, exploratory components, which require separate informed consent for subjects agreeing to participate in these.

The first cohort will comprise 4 groups of 2 subjects each. Subjects will be administered single oral doses of OZ439 and PQP in combination. The dose of OZ439 and PQP will be different for each group in Cohort 1, and subjects will be randomised into one of the dose groups listed in Table 1.

Table 1 OZ439 and PQP Cohort 1 Dose

Drug	Dose group			
	1A	1B	1C	1D
OZ439(mg)	200	200	400	400
PQP(mg)	480	640	480	640

The data captured from this first cohort will be used to determine the relationship between OZ439 and PQP concentrations and parasitaemia levels. Based on safety and tolerability data up to Day 42±2 and PK/PD analysis outcomes (based on PD data up to Day 42 and PK data up to Day 35±2), of the drugs given in combination, the dose(s) for the subsequent cohort will be determined.

After review of the PK/PD and safety data from Cohort 1 by SDR, it was determined that, the second cohort will be composed of 2 dose groups of 4 subjects. Subjects will be randomised into one of 2 dose groups and administered single oral doses of OZ439 and PQP in combination. The combined dose of OZ439 and PQP will be different for each group in this cohort as shown in Table 2.

Table 2 OZ439 and PQP Cohort 2 Dose

Drug	Dose group	
	2A	2B
OZ439(mg)	800	200
PQP (mg)	960	320

A similar analysis will be done at the end of cohort 2 combining cohort 1 and 2 data to decide the dose(s) to be tested in cohort 3. This will be decided by the funding sponsor and the Principal Investigator following SDRT and scientific evaluation.

The doses used in all Cohorts will not exceed 800 mg for OZ439 and 1440 mg for PQP as determined in previous safety, pilot efficacy and phase 2 studies. Each subject will be inoculated on Day 0 with approximately 2,800 viable parasites of *P. falciparum* infected human erythrocytes administered intravenously. Subjects will be monitored daily via phone call/text message on Days 1 to 3 post-inoculation to solicit any AEs.

Then, subjects will come to the clinical unit on a daily basis from Day 4 until the presence of asexual parasites is established by qPCR targeting the 18S rRNA gene (referred to as malaria 18S qPCR). Once qPCR becomes positive and until OZ439 and PQP administration, subjects will attend the clinical unit for twice-daily visits, separated by approximately 12 hours, for clinical evaluation and blood sampling.

Subjects will be admitted to the clinical unit for single dose administration of OZ439 and PQP 8 days after malaria inoculation or earlier if a subject has a malaria clinical score  $> 6$  at Investigator's discretion. An intravenous cannula will be placed and preliminary blood samples collected. The participants will then be administered the IMP in a fasting state immediately. Subjects in the first cohort may all be dosed on the same day, as these exposures have been documented in previous studies and shown to be well tolerated.

Once single dose administration of OZ439 and PQP occurs, subjects will be followed up as inpatients for at least 72 hours to monitor for safety and tolerability of the treatment and to ensure adequate clinical and parasitological response. Blood samples will be collected pre-dose and following OZ439 and PQP treatment to measure plasma concentrations of OZ439 and PQP. Wherever possible, PK sampling will coincide with post-dose blood collection for monitoring of parasitaemia.

After 72 hours, if clinically well, subjects will be discharged from the clinical unit and will be followed up regularly for safety assessments, PK sampling, clinical evaluation and malaria qPCR blood sampling until Day 42±2. All subjects will receive a standard course of therapy with

Riamet® (artemetherlumefantrine) on Day 42±2 or earlier in the event of failure of clearance of parasitaemia defined as failure to clear parasitaemia by at least 10^4 at 72 hours post-IMP administration. Riamet will also be administered in the event of recrudescence of parasitaemia (defined as  $\geq 5,000$  blood stage parasites/mL and a 2-fold increase within 48 hours, or a malaria clinical score  $> 5$ ) or at Investigator's discretion. If indicated by the presence of gametocytes at the time of treatment with Riamet®, Primacin™ 45 mg will also be administered as a single oral dose.

Subjects participating may optionally consent to be included in the exploratory components of the study which require additional blood samples to be collected at specified points throughout the study. These time points coincide with those already scheduled as part of the main study assessments. If any of the main study time points change the exploratory study time points will change to match. Details of the exploratory components and analyses are provided in Section 7.2.2.

A review by the SDRT of data from each cohort will be conducted prior to dosing the subsequent cohort. Safety and tolerability data up to Day 42±2 and PK/PD analysis outcomes (based on PD data up to Day 42±2 and PK data up to Day 35±2), from all subjects who received treatment with OZ439 and PQP will be required for the review. A similar analysis will be done at the end of cohort 2 combining cohort 1 and 2 data to decide the dose to be tested in cohort 3. This will be decided by the funding sponsor and the Principal Investigator following review of the data by the SDRT and scientific evaluation.

The doses used in all cohorts will not exceed the maximum acceptable doses predefined for this study (800 mg for OZ439 and 1440 mg for PQP) as determined in previous safety, efficacy and phase 2 studies.

## 4.2 STUDY ENDPOINTS

### 4.2.1 PRIMARY ENDPOINT

- The PK/PD relationship between OZ439 and PQP plasma concentrations and blood stage asexual parasitaemia will be determined by:
  - Effect of OZ439 on  $E_{max}$  and  $EC_{50}$  of PQP
  - Effect of PQP on  $E_{max}$  and  $EC_{50}$  of OZ439
- The safety and tolerability of a single combined dose of OZ439 and PQP will be evaluated by the incidence, severity and relationship of observed and reported AEs up to trial Day 42±2 after the co-administration of single doses of OZ439 and PQP to subjects inoculated with IBSM.

### 4.2.2 SECONDARY ENDPOINTS

- Estimation of OZ439 and PQP PK parameters up to trial Day 42 after coadministration of single doses using non-compartmental methods:  $AUC_{0-168h}$ ,  $AUC_{last}$ ,  $AUC_{0-inf}$ ,  $C_{max}$ ,  $t_{max}$ ,  $t_{1/2}$ ,  $t_{lag}$ ,  $C_{168h}$ ,  $CL/F$ ,  $Vz/F$  and  $\lambda_{inf}$ .
- The effect of coadministered single oral doses of OZ439 and PQP on clearance of *P. falciparum* blood stage parasites from the blood of inoculated subjects as measured by qPCR up to trial Day 42 after coadministration of OZ439 and PQP. Parasite clearance will be assessed by the following parameters:
  - Parasite clearance half-life ( $Pt_{1/2}$ ).
  - Parasite reduction ratio (PRR)
  - Percentage of subjects with recrudescence of parasitaemia  $\geq 5000$  blood stage parasites/mL and a fold increase within 48 hours, or occurrence of malaria symptoms with a malaria clinical score  $> 6$

---

#### 4.2.3 EXPLORATORY ENDPOINTS

- Identification of immune checkpoint molecules.
- The level of expression of complement regulatory proteins (CD35, CD55 and CD59) and phosphatidylserine on RBC.
- The level of complement activating antibodies and phosphatidylserine antibodies.

## 5 STUDY ENROLLMENT AND WITHDRAWAL

### 5.1 SUBJECT INCLUSION CRITERIA

Subjects eligible for inclusion in this study must fulfill the following criteria:

#### Demography

1. Adult (male and female) subjects between 18 and 55 years of age inclusive, who do not live alone (from inoculation day until at least the end of Rhamet® treatment) and will be contactable and available for the duration of the trial and contactable up to 2 weeks following the End of Study visit (approximately 5 weeks).
2. Body weight minimum 50 kg, body mass index between 18 and 32, kg/m^2 inclusive.

#### Health status

3. Certified as healthy by a comprehensive clinical assessment (detailed medical history, complete physical examination and special investigations)
4. Vital signs after 5 minutes resting in supine position:
  - 90 mmHg ≤ systolic blood pressure (SBP) ≤ 140 mmHg,
  - 40 mmHg ≤ diastolic blood pressure (DBP) ≤ 90 mmHg,
  - 40 bpm ≤ heart rate (HR) ≤ 100 bpm.
5. Must have QTcF ≤ 450 ms, QTcB ≤ 450 ms for male subjects, QTcF ≤ 470 ms, QTcB ≤ 470 ms for female subjects and PR interval ≤ 210 ms at screening and at pre-inoculation or inoculation day.
6. Heterosexual women of childbearing potential should be surgically sterile or using an insertable, injectable, transdermal or combination oral contraceptive approved by the TGA combined with a barrier contraceptive for the duration of the study, and have negative results on a urine pregnancy test done before inoculation. Abstinent, heterosexual male subjects must agree to start a double method if they start a sexual relationship during the study. Adequate contraception does not apply to subjects of childbearing potential with same sex partners (abstinence from penile vaginal intercourse), when it is their preferred and usual lifestyle. Female subjects with same sex partners must not be planning fertilisation within the required contraception period.

Women of non-childbearing potential who will not require contraception during the study are defined as: postmenopausal (spontaneous amenorrhoea for ≥ 12 months, or spontaneous

amenorrhoea for ~~6~~ 2 months and follicle stimulating hormone (FSH)  $\geq$  40 IU/mL; either should be together with the absence of oral contraceptive use for > 12 months).

Male subjects participating must agree to use a ~~double~~ barrier method of contraception including condom plus diaphragm or condom plus intrauterine device or ~~condom~~ ~~sterile~~ oral/transdermal/injectable hormonal contraceptive by the female partner from the time of informed consent through to 90 days after the last dose of OZ439 and PQP. Abstinent male subjects must agree to start a ~~double~~ barrier method if they begin ~~sexual~~ relationships during the study and up to 90 days after the last dose of study drug.

Male subjects with female partners that are surgically ~~sterile~~ male subjects who have undergone sterilisation and have had testing to confirm the success of ~~sterilisation~~ may also be included.

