In healthy subjects treated with OZ439 alone or OZ439 in combination with PQP, gastrointestinal (GI) symptoms which include nausea, vomiting, and diarrhea, are the most commonly reported AEs and these AEs have been reported to be generally mild in intensity. OZ439 was clinically well tolerated in two previous IBSM studies (QP12C10 and QP14C12) where the highest dose tested was 500 mg. In a Phase I IBSM study QP12C10 in healthy subjects infected with *P. falciparum*, most of the AEs reported were assessed as probably related to the inoculum (i. e., malaria). There were no events considered probably related to OZ439. In another Phase I IBSM study QP14C12, healthy subjects infected with *P. falciparum* received OZ439 in combination with another investigational antimalarial, DSM265. No new clinically relevant safety signals were observed. OZ439 may be contraindicated in persons with known hypersensitivity to artemisinin compounds or to any components of the product formulation. Carcinogenicity studies have been performed with OZ439. OZ439 has shown in vivo embryofetal toxicity in the rat. Therefore, OZ439 should not be administered to pregnant or breastfeeding women. However, OZ439 can be administered to women of child bearing potential (WOCBP) with use of a strict double method of contraception in well controlled clinical trials and under medical supervision. Healthy male and female subjects participating in studies of OZ439 must agree to use a double method of contraception for a duration defined in section 5 (Inclusion criteria) of this protocol.

No deaths have been reported in any of the clinical studies.

Additional information on nonclinical and clinical studies conducted with OZ439 is provided in the IB [38].

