## Interfering substances

26. Any vaccination within the last 28 days.
27. Any corticosteroids, anti-inflammatory drugs, immunomodulators or anticoagulants. Any subject currently receiving or having previously received immunosuppressive therapy (including systemic steroids, adrenocorticotrophic hormone or inhaled steroids) at a dose or duration associated with hypothalamic-pituitary-adrenal axis suppression (e.g. 1 mg/kg/day prednisone, chronic use of inhaled high potency corticosteroids such as budesonide 800 µg/day or fluticasone 750 µg, or equivalent).
28. Any recent (<6 weeks) or current systemic therapy with an antibiotic or drug with potential antimalarial activity (e.g. chloroquine, piperazine phosphate, benzodiazepine, flunarizine, fluoxetine, tetracycline, azithromycin, clindamycin, doxycycline etc.).
29. Ingestion of any poppy seeds within the 24 hours prior to the screening blood test (subject will be advised by phone not to consume any poppy seeds in this time period).
30. Excessive consumption of beverages or food containing xanthine bases including Red Bull, chocolate, coffee etc. (more than 400 mg caffeine per day, equivalent to more than 4 cups of coffee per day).
31. Unwillingness to abstain from consumption of grapefruit or Seville oranges from inoculation day until end of the study
32. Unwillingness to abstain from consumption of quinine containing foods/beverages such as tonic water and lemon bitter, from inoculation day until end of the study.
33. Use of prescription drugs or non-prescription drugs or herbal supplements (such as St John's Wort), within 14 days or 5 half-lives (whichever is longer) prior to the malaria inoculation. As an exception, ibuprofen (preferred) may be used at doses of up to 1.2 g/day paracetamol at doses of up to 4g/day after discussion with the investigator. Limited use of other non-prescription medications or dietary supplements, not believed to affect subject safety or the overall results of the study, may be permitted on a case-by-case basis following approval by the Sponsor in consultation with the investigator. Subjects are requested to refrain from taking non-approved concomitant medications from recruitment until the conclusion of the study.

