### 5.3 CONTRACEPTION

Male and female subjects who are sexually active must use, with their partner, 2 approved methods of highly effective contraception from the time of informed consent until 90 days after the last dose of OZ439 and PQP.

Two or more of the following methods are acceptable and must include at least 1 barrier method:

- Surgical sterilisation (vasectomy (male), tubal ligation (female))
- Placement of an intrauterine device or intrauterine system
- Hormonal contraception (implantable, patch, oral, injectable)
- Barrier methods (this must be a condom or their partner's use of an occlusive cap [diaphragm or cervical/vault caps] with spermicidal foam/gel/film/cream/suppository)

Alternatively, true abstinence is acceptable when it is in line with the subject's preferred and usual lifestyle. If a subject is usually not sexually active but becomes active, they, with their partner, must comply with the contraceptive requirements detailed above.

Adequate contraception does not apply to subjects of childbearing potential with same sex partners (abstinence from penile/vaginal intercourse), when this is their preferred and usual lifestyle. Female subjects with same sex partners must not be planning in vitro fertilisation within the required contraception period.

Women of non-childbearing potential who will not require contraception during the study are defined as: postmenopausal (spontaneous amenorrhoea for  $\geq 12$  months, or spontaneous amenorrhoea for 6-12 months and follicle stimulating hormone (FSH)  $\geq 40$  IU/mL; either should be together with the absence of oral contraceptive use for  $> 12$  months) or permanently sterilised (e.g. hysterectomy, bilateral salpingectomy).

Adequate contraception is also not required for female subjects with female partners that are permanently sterilised or male subjects who have undergone sterilisation and have had testing to confirm the success of the sterilisation.

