### 8.4.5 REPORTING OF PREGNANCY

Pregnancy in a female subject or a male subject's female partner during the study should be reported and followed as described beneath. Pregnancy does not constitute an SAE and the pregnancy outcome will not be recorded in the eCRF unless it is considered to be an SAE.

The Investigator must notify Prime Vigilance, in an expedited manner of any pregnancy occurring from the date of informed consent signature up to 90 days after administration of Z439 and PQP. The same process as described for AEs and AESI as described in Section 8.4.2 should be followed. In all cases, the pregnancy must be followed until birth of the child, and the outcome of the pregnancy and birth reported as above by completing appropriate section of the Pregnancy Report Form used for the initial notification. The timelines of the outcome reporting vary as follows:

- Normal outcomes should be reported within 45 days of birth/delivery
- Abnormal outcomes should be reported in an expedited manner as described in Section 8.4.2.

An additional SAE Report form must be completed if the subject or subject's partner sustains a serious event. A Parent/Child/Foetus Report (PCFR) must be completed if the child/foetus sustains an event.

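### The protocol gives women two contraception end dates about 53 days apart, and exclusion 33 has no exception for the prescription contraceptives that inclusion 6 accepts

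*Protocol*

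**What the plan says.** **Duration.** In Protocol Section 5.1, inclusion criterion 6 names the methods that qualify a woman of childbearing potential: surgical sterility, or an insertable, injectable or transdermal method or a "combination oral contraceptive approved by the TGA combined with a barrier contraceptive for the duration of the study". The same criterion binds men "from the time of informed consent through to 90 days after the last dose of OZ439 and PQP". Section 5.3 makes no difference between the sexes and requires "2 approved methods of highly effective contraception from the time of informed consent until 90 days after the last dose of OZ439 and PQP".

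Two paragraphs of Section 2.3.1 tell the reader where to look. The OZ439 risk text says that subjects of both sexes "must agree to use a double method of contraception for a duration defined in section 5 (Inclusion criteria) of this protocol". The paragraph on reactions to the blood sample refers to Section 5.1 for the contraception rules that apply to women of childbearing potential during the study. Section 8.4.5 requires notification of any pregnancy "occurring from the date of informed consent signature up to 90 days after administration of" the study drugs.

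**Medication.** Exclusion criterion 33 in Section 5.2 covers "Use of prescription drugs or non-prescription drugs or herbal supplements" within 14 days or 5 half-lives of inoculation, whichever is longer. Its exceptions are ibuprofen, paracetamol and, case by case, other non-prescription products or supplements. Section 5.2 closes by ruling out waivers. Section 7.5 says that permitted medications are those set out in Sections 5.1 and 5.2.

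**The concern.** The OZ439 risk text reports embryofetal toxicity in the rat and makes strict double contraception a condition for including women of childbearing potential. The length of that commitment should therefore be the same wherever it is stated. Instead, women have one end date in the numbered inclusion criterion and a later one in Section 5.3, and both cross-references in Section 2.3.1 lead to the criterion with the earlier date.

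Eligibility is verified against the inclusion and exclusion criteria at screening and again on Day 0 (Sections 7.3.1 and 7.3.2). Section 5.3 is not a numbered criterion, so a woman could pass every checked item on the shorter commitment.

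On medication, the same woman could meet inclusion 6 by using a prescription pill, patch or injection and, for that reason, meet exclusion 33. The SAP (Section 6.4) lists eligibility violations, so the ambiguity affects how subjects are classified as well as who is admitted.

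**Working it through.** **Inputs**
- Dosing: Day 8, or earlier in some circumstances (Protocol Section 4.1).
- End of Study visit: Day 45±2 (Section 7.3.4).
- Follow-up after dosing: 37 days, within about 74 days of participation (Protocol Summary).
- Contraception for women: to study end (inclusion 6) or 90 days after dosing (Section 5.3).

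**1. Reproduce the plan's own figures.** Follow-up after dosing = 45 − 8 = 37 days, as stated. Participation from Day −28 to Day 45 inclusive = 28 + 1 + 45 = 74 days, as stated. Study end for a subject can therefore be taken as the End of Study visit.

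**2. Gap between the two end dates.** Gap = 90 − (End of Study day − dosing day).

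| End of Study visit | Days after a Day 8 dose | Gap to 90 days |
|---|---|---|
| Day 43 | 35 | 55 |
| Day 45 | 37 | 53 |
| Day 47 | 39 | 51 |

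Ninety days after a Day 8 dose is trial Day 8 + 90 = 98.

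**3. Earlier dosing.** Suppose dosing falls on Days 4 to 7 (assumed) and the End of Study window does not move. The gap then runs from 90 − (47 − 4) = 47 days to 90 − (43 − 7) = 54 days. The size changes little.

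**4. Exclusion 33 against inclusion 6.** Taking the methods in turn:
- *Prescription injectable, transdermal or oral contraceptive.* Qualifies under inclusion 6. It is a prescription drug in current use, so it falls within the window of exclusion 33, and none of the listed exceptions covers it. The subject is ineligible on a literal reading.
- *Surgical sterility, postmenopausal status or same-sex partner.* No drug is involved, so exclusion 33 does not apply.
- *Non-drug device with a barrier.* Inclusion 6 accepts an insertable method without saying whether it must be hormonal, and Section 5.3 accepts an intrauterine device. Exclusion 33 does not apply to a device without drug.

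**5. Can another section settle it?** Section 7.5 refers to Sections 5.1 and 5.2 together, and these are the two sections that conflict. The bar on waivers removes the other way out.

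**The case against.** The strongest reply on duration is that Section 5.3 is mandatory for both sexes and lies within Section 5, and that inclusion 6 itself mentions a required contraception period. A woman who follows Section 5.3 satisfies both texts. This stands to a point: a reader might infer that women have no obligation after the End of Study visit, and the documents do not support that. It does not remove the contradiction, because the OZ439 risk text names the inclusion criteria specifically as the source of the duration.

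On exclusion 33, the reply is that Section 5.3 lists hormonal contraception as acceptable and that Section 7.5 lets a method named in Section 5.1 be read as permitted. That is a sensible reading of the intent, and an investigator may well have taken it. It still has to be inferred against the wording of exclusion 33.

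Two further inferences are tempting and fail:
- *The contact period is an error.* Inclusion 1 asks that subjects be "contactable up to 2 weeks following the End of Study visit", which is 45 + 14 − 8 = 51 days after dosing and 39 days short of 90. But this is a minimum condition for entry. It does not stop later contact, and Section 8.4.5 separately obliges the investigator to report pregnancies to 90 days. The two do not contradict each other.
- *Residual piperaquine shows the harm.* The protocol gives piperaquine a half-life of 4–5 weeks, so some would remain at study end. The embryofetal finding, however, is stated for OZ439, whose half-life is given as 46–62 h. At 37 days (888 h), between 888/62 ≈ 14 and 888/46 ≈ 19 half-lives have passed. Piperaquine retention therefore does not measure the stated risk.

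**Conclusion.** There are two internal inconsistencies, both of which should be fixed.

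1. The contraception period for women ends about 53 days earlier in inclusion 6 than in Section 5.3 (51 to 55 days with the visit window; 47 to 54 if dosing is on Days 4 to 7). This assumes that a subject's study ends at her End of Study visit, as the stated 37 and 74 days imply.
2. On a literal reading, exclusion 33 makes users of prescription hormonal contraception ineligible, although inclusion 6 accepts their methods.

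A reader might go further and conclude that women can be enrolled only as eligibility violations. That does not follow. Inclusion 6 offers hormonal methods as options and does not require them, and the groups in step 4 who use no drug are untouched by exclusion 33.

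The sample size (24, without a formal power calculation) and all planned analyses of endpoints are unaffected. What is at stake is the clarity of a safety commitment by healthy volunteers and of eligibility classification. The consent form was not available for this review, so it is unknown which duration women were told.

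**What to change.** - Reconcile inclusion 6, Section 5.3 and the two cross-references in Section 2.3.1 (reactions to the blood sample; OZ439 risks) so that one contraception duration applies to women throughout, and check that the consent form states the same one.
- Reconcile inclusion 6, exclusion 33 and Section 7.5 so that the status of contraceptives under exclusion 33 is explicit.
- Since the SAP (Section 2.4) reports 24 subjects already enrolled, check which duration enrolled women agreed to, and state how users of hormonal contraception were classified in the listing of eligibility violations.

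Which duration or medication rule is right is for the sponsor to decide. The cost is protocol wording, consent wording if it differs, and a short check of records. No visit, procedure or analysis is added.
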